4.1.2 Procedures for randomisation

On signing the Informed Consent the patients will be enrolled (enrolment = the process of allocating a unique identifier to a patient on entry into a clinical study, after obtaining written Informed Consent) and identified with a unique enrolment code (E-code) of 4 digits where the first digit is the site number and the three following the patient number. Uppsala=1, Malmö=2, Gävle=3, Västerås=4, Karlstad=5, Falun=6, and Umeå=7.

Enrolment will take place before treatment randomisation (randomisation = the assignment of patients to treatment in a clinical study according to a randomisation schedule generated by a random process) to assure allocation concealment. A randomisation list will be generated using a computerized procedure, by sorting 275 treatment allocations in each arm in random order using Excel (Microsoft, WA, USA). A total of 550 treatment allocations will be generated to accommodate possible erroneous entries to the database. Patients will be randomised strictly sequentially as they are eligible for randomisation. Simple randomization will be used without stratification given the large number of subjects.

The patients will be randomized on a 1:1 schedule to; metformin tablets in incremental doses to 2g daily *or* standard care.

If a patient discontinues from the study, the patient number will not be reused, and the patient will not be allowed to re-enter the study.

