5.1 Study measurements

5.1.1 Clinical data

At the enrolment visit the patients will undergo a clinical examination which consists of; recording of demographic data (date of birth, sex and ethnicity), medical history and concomitant diseases, smoking status, heredity of AAA, current medication, recording of weight & height, heart rate & blood pressure, cardio-pulmonary status and general appearance.

At all points of contact with phone or visit at the clinic any AE and SAE are recorded, target dose of study drug is determined and compliance is asked for. Discontinuation (temporarily or permanent) of study medication ≥ 3 consecutive days will be recorded.

At visits medical events and any changes in smoking status will be noted and vital signs and weight is recorded. Compliance to study drug is noted and remaining tablets are counted. At completion visit and at 24 months, the above plus a physical examination is performed. Changes in current medication are recorded yearly.

At enrolment visit, at 24 months and completion quality of life will be recorded with EQ-5D and RAND -36, see appendix 1.

At enrolment blood samples will be taken for fP-Glc and P-Creatinine, analysed at accredited hospital laboratory. P-Creatinine will be tested for safety every 12 months. A 24 months S-B12 is controlled for possible metformin induced deficiency. In Uppsala and Malmö venous blood samples will be taken at baseline, 24 months and completion for scientific reasons.

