8.3 Statistical analysis

The primary efficacy end-point is the between groups difference in mean annual AAA growth over 60 months. AAA growth will be analysed using an analysis of covariance (ANCOVA) model where AAA growth at 60 months is the dependent variable and treatment group and baseline AAA is included as independent variables. The results will be presented as the estimated group difference with 95 % confidence intervals at 60 months.

Similar methods will be used to assess growth as log transformed CT-volume and ultrasound diameter. Analysis of other outcomes: 1) Laboratory data and perivascular adipose tissue are exploratory endpoints and will be reported with descriptive statistics and evaluated with appropriate inferential statistics, 2) Patient reported outcome (QoL questionnaires) will be analysed using non-parametric test (Wilcoxson rank-sum test), 3) Pre-defined clinical events,

such as AAA-repair, rupture and death, are expected to be few, and the presentations will use descriptive statistics, 4) Economic analysis: Will be performed adopting a health system perspective. The cost-effectiveness analysis will produce an incremental cost effectiveness ratio as an estimated cost per surgical procedure avoided.

Handling of missing values: The primary analyses will be performed among patients with a measured value at the specific time point. However, as the number of missing values might be substantial several sensitivity analyses of the primary analysis will be performed:

- Multiple imputation (with different assumptions)
 - Assume that drop-outs respond according to randomized group
 - Assume that drop-outs respond according to control group
- Fixed imputation depending on reason for drop-out
 - For clinical events, such as AAA-repair, rupture and death, impute worst possible value
 - For other events impute using a maximum likelihood function

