8.4 Sample size estimation

Based on in house data and original data from an Australian study of the relationship between metformin and AAA growth (Golledge 2017) it is conservatively estimated that metformin treatment will lead to a 30% reduction in annual AAA growth. This is regarded as a meaningful change which is likely to translate to an important reduction in requirement for AAA repair. MRI data from the Uppsala group show a mean growth rate of 3mm/year, SD 2.17. Thus needing 184 patients for 80% power at a 30% reduced growth rate. CT data will likely show 10-15% larger SD, adding a 30% dropout rate over five years we approximate a need to recruit 500 patients, 250 in each arm, for 80% power at 2-tailed α 0.05.

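### The primary ANCOVA could also adjust for sex and smoking status, both already recorded at enrolment; this is an optional precision gain of uncertain size, not an error

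*Combined protocol and SAP*

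**What the plan says.** Section 8.3 analyses growth at 60 months by ANCOVA, where "treatment group and baseline AAA is included as independent variables". I read the baseline term as baseline diameter for the primary endpoint. Similar methods are planned for log-transformed CT volume and ultrasound diameter, and Section 10 applies ANCOVA to the same three measures at the 24-month interim analysis. The sensitivity analyses in Section 8.3 all concern missing values; none changes the covariates.

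On allocation, Section 4.1.2 states: "Simple randomization will be used without stratification given the large number of subjects".

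On data collected before allocation, Section 5.1.1 lists demographics (which include sex) at the enrolment visit, followed by "medical history and concomitant diseases, smoking status, heredity of AAA". Table 1 in Section 2.1 agrees: demographics and smoking status are marked at enrolment, and randomisation at the later baseline visit.

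**The concern.** Neither the randomisation nor the primary model takes account of sex or smoking, although both are known for everyone before treatment starts. In a linear model, a baseline variable that predicts the outcome removes residual variance. The confidence interval for the treatment difference then narrows, and the estimate is corrected for chance imbalance in that variable. If the covariates are fixed in advance, the type I error rate is unaffected. What is at stake is a somewhat sharper estimate at 60 months, and at the interim analysis, from data the trial already holds.

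There is also a reason to settle the covariates early. The trial is open label, the investigators do the analyses (Section 8) and the principal investigator may access the data at any time (Section 7.1). A covariate set written down now is more credible than one chosen after results are known.

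**Working it through.** **Inputs from Section 8.4.**
- Effect: "metformin treatment will lead to a 30% reduction in annual AAA growth".
- Control growth and spread: "MRI data from the Uppsala group show a mean growth rate of 3mm/year, SD 2.17". The planned difference is therefore 0.30 × 3 = 0.9 mm/year.
- CT spread: "CT data will likely show 10-15% larger SD". This gives 2.17 × 1.10 = 2.387 to 2.17 × 1.15 = 2.4955 mm/year.
- Attrition: "adding a 30% dropout rate over five years". This leaves 500 × 0.70 = 350 completers, taken as 175 per arm.
- Error rates: "for 80% power at 2-tailed α 0.05".

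**Reproducing the plan's figure.** n per arm = 2 × (1.960 + 0.842)² × 2.17² / 0.9² = 91.3, rounded up to 92, or 184 in total. This matches Section 8.4. The CT inflation raises the total to 222-242 completers, and dividing by 0.70 gives 318-346 to recruit. The planned 500 is above that, on the conservative side, and Section 8.4 calls it an approximation.

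**Power without extra covariates.** Power = Φ(0.9 / (SD × √(2/175)) − 1.96). This gives 94.1% at SD 2.387 and 92.1% at SD 2.4955.

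**Effect of adjustment.** Let R² be the share of growth variance that sex and smoking explain beyond baseline diameter. The documents give no value, so 0-10% is assumed. The SDs above are used as if they were residual after baseline diameter; Section 8.4 does not describe them as adjusted. The standard error is multiplied by √(1 − R²), and 350 completers become worth 350 / (1 − R²).

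| R² (assumed) | Fall in SE | Equivalent completers | Power, SD 2.387 | Power, SD 2.4955 | 95% CI half-width, SD 2.4955 (mm/year) |
|---|---|---|---|---|---|
| 0% | 0% | 350 | 94.1% | 92.1% | 0.523 |
| 2% | 1.0% | 357 (+7) | 94.6% | 92.6% | 0.518 |
| 5% | 2.5% | 368 (+18) | 95.1% | 93.3% | 0.510 |
| 10% | 5.1% | 389 (+39) | 96.1% | 94.5% | 0.496 |

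The largest power gain is 94.5 − 92.1 = about 2.4 points.

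**Is 10% a reasonable ceiling?** A binary covariate with prevalence p and growth difference D explains p(1 − p)D² / SD². With SD 2.4955 and assumed p of 10-40% and D of 0.3-1.0 mm/year, this runs from 0.1% (p = 0.1, D = 0.3) to 3.9% (p = 0.4, D = 1.0). Two such uncorrelated covariates reach at most about 7.7%.

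**Chance imbalance.** With p = 20% and D = 0.5 mm/year (both assumed), the 95% range for the difference in prevalence between arms is ±1.96 × √(2 × 0.2 × 0.8 / 175) = ±8.4 percentage points. That moves the treatment estimate by at most 0.084 × 0.5 = about 0.04 mm/year, against a planned effect of 0.9.

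**A smaller true effect.** At 0.6 mm/year (a 20% reduction) and SD 2.4955, power is 61.4% without adjustment. It becomes 62.2%, 63.6% and 65.9% at R² of 2%, 5% and 10%.

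**Price if the covariates predict nothing.** Sex takes one degree of freedom and three smoking categories take two. Residual degrees of freedom go from 347 to 344, so the standard error rises by roughly √(347/344) − 1 = 0.4%. The table leaves this out. It is close to neutral.

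**The case against.** The strongest objection is that the key premise is not in the documents. Adjustment helps only if sex and smoking predict growth rate given baseline diameter, and no section says that they do. This stands, and it is why the gain is given as a range starting at zero.

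A reader might infer the premise from the protocol's handling of these variables, but the text does not carry it. The sex-specific entry limits parallel the sex-specific repair thresholds in Section 1.1, so they concern when to operate, not how fast the aneurysm grows. Smoking cessation appears in Section 4.1 among general cardiovascular measures. Smoking recorded at later visits is post-randomisation data and could not serve as a baseline covariate.

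Two stronger readings also fail. One is that unstratified randomisation makes the planned comparison biased or requires adjustment. It does neither: randomisation protects the test, and the model already includes the baseline value. The other is that the 44 mm limit for women entangles sex with diameter in the model. Sex is not in the model, so nothing is entangled; any correlation would only reduce what sex adds.

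It can also be asked why these two covariates and not age, site or medication. That is a fair question of choice, and it is best settled by fixing a short list with defined categories now.

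**Conclusion.** The plan is valid as written; this is a minor optional improvement. The factual basis is secure: one baseline covariate, no stratification, and sex and smoking recorded for all before allocation. The size of the benefit is not secure. Under the assumed 0-10% of residual variance explained, the standard error falls by 0-5%, equivalent to 0-39 completers beyond 350, with at most about 2.4 points of power at 0.9 mm/year. The benefit would count for somewhat more if the true effect were smaller than planned or dropout exceeded 30%. The case for acting rests on the very low cost and on having the covariates fixed in advance, not on any defect in the present model.

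**What to change.** In Section 8.3, before any outcome data are seen, add sex and smoking status at enrolment as covariates in the primary ANCOVA. Use fixed smoking categories, for example never, former and current, and say how a missing smoking status is handled. Apply the same covariates to the CT-volume and ultrasound-diameter models, and state in Section 10 that the interim ANCOVAs use them too. Keep the model with baseline diameter only as a named sensitivity analysis.

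The cost is a line or two of text and three degrees of freedom out of about 350. No new data, visits or change to the sample size are needed.

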1.2.2 Secondary objectives

To examine if metformin limits increase in; a) CT-assessed AAA volume; b) ultrasound assessed AAA diameter; c) improves health-related quality of life; d) reduces the need for surgery (diameter ≥55mm) or rupture; and e) represents a cost-effective treatment to reduce the need for AAA surgery.

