8.2.2 Secondary variables

Secondary efficacy variables are; 1) difference in log-transformed AAA-volume determined by CT at 24 and 60 months vs at baseline (Log-transformation is undertaken because AAA volumes appear to follow a right-skewed distribution based on in house data), 2) difference in AAA-diameter determined by US at 24 and 60 months vs at baseline, 3) difference in circulating inflammation and matrix remodelling biomarkers assessed by established assays, 4) difference in quality of life score at 24 and 60 months vs at baseline, 5) difference in need for AAA surgery and aneurysm rupture at 24 and 60 months and 6) cost effectiveness of metformin treatment 2 g daily to reduce need for prophylactic surgery of AAA.

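### The quality-of-life change from baseline is tested by a rank-sum test without baseline adjustment, and no effect estimate or confidence interval is planned

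*Combined protocol and SAP*

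**What the plan says.** Section 1.2.2 lists quality of life among the secondary objectives: "c) improves health-related quality of life". The data are collected for this. Section 5.1.1 states: "At enrolment visit, at 24 months and completion quality of life will be recorded with EQ-5D and RAND -36", and Table 1 schedules the questionnaires at the same three points in both arms.

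Section 8.2.2 defines the variable as "difference in quality of life score at 24 and 60 months vs at baseline". Section 8.3 then gives the analysis: "Patient reported outcome (QoL questionnaires) will be analysed using non-parametric test (Wilcoxson rank-sum test". It names no covariate, effect measure or interval, and does not repeat that the test is applied to the change.

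The same section treats CT diameter differently. It specifies an ANCOVA in which "treatment group and baseline AAA is included as independent variables", and adds: "The results will be presented as the estimated group difference with 95 % confidence intervals at 60 months". The extension to other outcomes is limited to imaging: "Similar methods will be used to assess growth as log transformed CT-volume and ultrasound diameter". No reason is given for handling quality of life otherwise.

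**The concern.** A change score with no covariate uses the baseline with a fixed coefficient of 1. When the correlation between baseline and follow-up is below 1 and the variances are similar, that coefficient is too large. The change then stays negatively associated with baseline, and this association is left in the error term. Fitting the baseline as a covariate removes it at no cost in data. Section 4.1.2 uses simple randomisation without stratification, so chance differences between arms in baseline quality of life are possible, and a covariate deals with them better than subtraction does.

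The second gap is in reporting. The objective asks whether metformin improves quality of life. A p-value alone does not show by how much, and a non-significant one cannot separate little effect from too little information. The health-economic analysis does not fill the gap, because it is expressed as cost per surgical procedure avoided. At stake is how informative one secondary objective will be.

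**Working it through.** **Plan's own figure.** The documents give no SD, effect size, correlation or power for quality of life, so there is no figure on this outcome to reproduce. The only sample-size figure concerns growth (section 8.4). With a difference of 0.3 × 3 = 0.9 mm/year, SD 2.17, two-sided α 0.05 and 80% power, n per arm = 2 × (1.960 + 0.842)² × 2.17² / 0.9² = 91.3, rounded up to 92. That is 184 in total, as stated.

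**Inputs.** From the documents: 250 per arm and 30% dropout, hence 250 × 0.7 = 175 per arm with data. Assumed: baseline to follow-up correlation ρ of 0.4 to 0.8, SD 1 at both times, normal scores, and a true difference of 0.25 SD for the power figures.

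**Variance.** The raw change has variance 2(1 − ρ). With baseline as covariate the residual variance is 1 − ρ². The ratio is (1 − ρ²) / [2(1 − ρ)] = (1 + ρ)/2.

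**Power.** Φ(0.25 / √(2V/175) − 1.96). For ANCOVA, V = 1 − ρ². For the rank-sum test on change, V = 2(1 − ρ)/0.955, where 0.955 = 3/π is the efficiency of the test for normal data.

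Example, ρ = 0.5:
- Rank-sum on change: V = 1/0.955 = 1.047, standard error √(2 × 1.047/175) = 0.109, and Φ(2.285 − 1.96) = 63%.
- ANCOVA: V = 0.75, standard error 0.0926, and Φ(2.700 − 1.96) = 77%.

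| ρ | Variance ratio, adjusted to raw change | Variance reduction | Power, rank-sum on change | Power, ANCOVA |
|---|---|---|---|---|
| 0.4 | 0.70 | 30% | 55% | 72% |
| 0.5 | 0.75 | 25% | 63% | 77% |
| 0.6 | 0.80 | 20% | 72% | 83% |
| 0.7 | 0.85 | 15% | 84% | 91% |
| 0.8 | 0.90 | 10% | 95% | 97% |

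Simulation with normal scores (3,000 runs at each of ρ = 0.5 and 0.7) agreed with the power formulas within about 2 points.

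**Other score shapes.** The formulas assume normality, so the comparison was also simulated with 175 per arm, a 0.25 SD difference and ρ = 0.5:

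| Scores | Rank-sum on change (planned) | Rank-based analysis of change, adjusted for baseline |
|---|---|---|
| Normal | 62% | 73% |
| Ceiling-limited | 52% | 65% |
| Heavy-tailed | 82% | 88% |

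With heavy tails plain ANCOVA reached 78%, below the planned test at 82%. The baseline-adjusted rank analysis matched or beat the planned test in every scenario tried for ρ from 0.4 to 0.8. The proportional-odds model was not simulated.

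**The case against.** The strongest defence has four parts.

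- **Baseline is already used.** A reader of 8.3 alone might infer that the baseline score is discarded and set the loss at 1 − (1 − ρ²) = ρ², or 16% to 64% for ρ from 0.4 to 0.8. Section 8.2.2 does not support that, because it defines the variable as a change. Only the loss against raw change applies, and it is small when ρ is high. This part stands in full.
- **The test is valid.** A reader might infer that raw change biases the comparison through regression to the mean. Under randomisation that effect is the same in both arms in expectation. The issue is efficiency, not validity. This also stands.
- **An estimate is not ruled out.** A reader might infer that the rank-sum test can give only a p-value. It can be reported with a Hodges-Lehmann shift and its interval. The text omits an effect measure but does not exclude one, so the fair statement is that none is planned.
- **Ranks suit these scores, and a fixed test has merit.** Skewed or ceiling-limited scores give a rank test some justification, and ANCOVA can lose to it with heavy tails. Choosing the model after looking at residuals would be a real weakness here, since the trial is open-label (section 2.1) and the investigators run the analyses (section 8). This argues against replacing the test with ANCOVA by default or leaving the model open. It does not argue against a baseline-adjusted rank-based or ordinal model fixed in advance.

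**Conclusion.** The point holds as a loss of precision and a gap in reporting for one secondary endpoint. As written, the plan tests the quality-of-life change without a covariate and commits to no estimate or interval, although the baseline score is scheduled for every patient and the imaging outcomes get both.

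The size rests on assumptions. With normal scores, equal variances and ρ between 0.4 and 0.8, adjustment lowers the variance by 30% down to 10% against raw change. For an assumed 0.25 SD difference with 175 per arm, power rises by 17 points at ρ = 0.4 (55% to 72%) but only 2 at ρ = 0.8 (95% to 97%). It is tempting to restate the 25% at ρ = 0.5 as a third more patients (1/0.75 = 1.33). The documents do not support that as a headline, because it depends on a single assumed correlation and on normal theory.

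The growth endpoint and the interim rule in section 10 do not use these scores, so neither is affected. The change is worth making but is not a condition for the trial's main conclusion.

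**What to change.** In section 8.3, replace the quality-of-life sentence with wording to this effect:

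- Each quality-of-life score at 24 and at 60 months is analysed with treatment group and the baseline score as covariates.
- One model is named in advance. A rank-based or proportional-odds model with baseline keeps the robustness of the planned test; ANCOVA is the alternative. The text should state whether the outcome is the change or the follow-up score. In ANCOVA with baseline as covariate the treatment estimate is the same for both, but in a rank-based or ordinal model it need not be.
- The effect measure belonging to that model (a shift or mean difference on the score scale, or an odds ratio) is reported with its 95% CI.
- The rank-sum test on the change defined in 8.2.2 is kept as a sensitivity analysis.

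The cost is wording only, with no new data or visits. The one small downside is that the model must be fixed before outcome data are seen, without knowing the shape of the scores. That favours the rank-based or ordinal option. The choice should be settled before the 24-month interim analysis.

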1. BACKGROUND, RATIONALE AND OBJECTIVES

1.1 Background

Abdominal aortic aneurysm (AAA) is a major health issue and ruptured AAA a common cause of death in Europe and North America. In Sweden 700-1000 annual deaths are attributed to AAA. To prevent rupture, early detection and preventive surgical repair in selected individuals is recommended. AAA screening programs are already implemented in the UK, Sweden and the USA. Most screening detected AAAs are, however, small (diameter 30-54 mm) and are under surveillance until expansion to the threshold for elective surgical repair; i.e. diameter ≥55 mm for men and ≥50 mm for women. Presently approximately 15,000 men and women are being monitored for small AAAs in Sweden, of whom 70% eventually will require surgical repair. In 2015, ~1200 AAA repairs were performed in Sweden at a cost of ~30 million Euros (Swedvasc 2016). AAA repair is associated with significant mortality (1-5%), perioperative complications (up to 20%), cost (~25,000 Euros/patient) and need for life-long post-operative follow-up, imaging and repeat surgery (in ~20% of cases) (Mani 2009, Mani 2010, Mani 2013).

A key limitation of contemporary treatment strategies of AAA is the lack of therapy directed at small AAA (Wanhainen 2019). Although surgical repair is an effective treatment for large AAA, several large trials (Powell JT 2007, UKSAT 2002, Lederle 2002, Cao 2011) have shown that early surgery of small AAA does not reduce mortality. Given that AAA diameter is the strongest predictor for rupture and the natural course for AAA is continued expansion, a mean to reduce AAA growth rate would be highly beneficial. Commonly used cardiovascular drugs, such as anti-platelet drugs, statins, angiotensin converting enzyme inhibitors and beta-blockers have not been shown to slow AAA growth in cohort studies (Ferguson 2010, Twine 2011). Previous interventional trials with therapy directed at AAA growth reduction include antibiotics, mast cell inhibitors, beta-blockers, platelet inhibitors, and angiotensin converting enzyme blockers, with trials of stem cells and cyclosporine under way. These trials have all been either small, with negative results or had unacceptable side effects (Meijer 2013, Sillesen 2015, PATI 2002, Golledge 2017, Rughani 2012).

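### Need for AAA surgery or rupture is a secondary efficacy question about a difference between arms, but section 8.3 plans description only, with no between-arm estimate or confidence interval

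*Combined protocol and SAP*

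**What the plan says.** Section 1.2.2, objective (d), is to examine whether metformin "reduces the need for surgery (diameter ≥55mm) or rupture". Section 8.2.2 carries this forward as secondary efficacy variable 5: "difference in need for AAA surgery and aneurysm rupture at 24 and 60 months". Items 1, 2 and 4 of that list are changes from baseline and item 5 is not, so a difference between the arms is its only workable reading.

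Section 8.3 assigns a method to each kind of outcome. Growth gets ANCOVA with a 95% CI, volume and ultrasound diameter get similar methods, and quality of life gets a rank-sum test. Even the exploratory laboratory and perivascular fat data get some form of inference. For clinical events the text is: "such as AAA-repair, rupture and death, are expected to be few, and the presentations will use descriptive statistics". The diameter-based need for surgery in objective (d) is not mentioned there.

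Two other parts of the plan use an event comparison. The cost-effectiveness ratio in section 8.3 is "an estimated cost per surgical procedure avoided". Section 10 ends the trial if there is significant harm on growth or on AAA related events, but names a method (ANCOVA) only for the three growth measures.

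**The concern.** A description by arm does not answer a question about reduction. Objective (d) is also the outcome closest to patients and payers: section 8.4 calls the 30% growth effect meaningful because it is a change "which is likely to translate to an important reduction in requirement for AAA repair".

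The event itself is not fixed for analysis. It could be repairs performed, diameter reached on CT, or diameter reached on ultrasound. Section 1.2.2 uses 55 mm for everyone, while section 1.1 gives 55 mm for men and 50 mm for women. Under section 8 the investigators analyse the data themselves, and the trial is open-label. If a comparison is wanted at the end, its measure and event definition could be chosen after the data are seen. The interim harm rule has the same gap, because significance on events cannot be judged from description.

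**Working it through.** **1. The plan's own figure.** Section 8.4 states: "MRI data from the Uppsala group show a mean growth rate of 3mm/year, SD 2.17". With a 30% reduction (0.9 mm/year), two-sided alpha 0.05 and 80% power:

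n per arm = 2 × [(1.960 + 0.842) × 2.17 / 0.9]² ≈ 91.3, rounded up to 92, so 184 in total. This matches the protocol. It concerns growth only; no event number, rate or power is stated anywhere.

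**2. What the growth inputs imply for diameter.**
- Control, 60 months: 3 × 5 = 15 mm. A patient growing at the mean rate reaches 55 mm if entry is at 55 − 15 = 40 mm or more. Section 3.1 allows entry up to 49 mm in men.
- Metformin, 60 months: 2.1 × 5 = 10.5 mm, so entry at 44.5 mm or more.
- Control, 24 months: 3 × 2 = 6 mm, so entry at 49 mm, the top of the permitted range.

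**3. Simulated crossings of 55 mm.** The protocol gives no baseline distribution, so four were assumed over 30–49 mm: uniform (mean 39.5 mm), decreasing triangular (36.3), truncated normal (38.4) and truncated exponential near 30 mm (34.0). Growth is linear within patient and normal between patients, with crossing time (55 − baseline)/growth. Loss is exponential, reaching 30% at five years. The threshold is 55 mm for all, because the share of women is not given. SD 2.17 is the protocol's; 1.0 and 0.5 are assumed, in case part of 2.17 is measurement error. The 2 mm/year rate is also assumed.

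| Control growth | SD | Crossings by 60 months, of 500 |
|---|---|---|
| 3 mm/year | 2.17 | 91–165 |
| 3 mm/year | 1.0 | 41–145 |
| 3 mm/year | 0.5 | 24–138 |
| 2 mm/year | 2.17 | 54–113 |
| 2 mm/year | 1.0 | 13–72 |
| 2 mm/year | 0.5 | 6–56 |

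By 24 months at 3 mm/year the counts are 4–32 (SD 2.17) and 1–12 (SD 1.0). A tighter assumed baseline (mean 32.5 mm) at 3 mm/year gives 73, 20 and 6 by 60 months at SD 2.17, 1.0 and 0.5, so the lower ends above are not floors.

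**4. An estimate is possible even with few events.** Assume 10% control risk and risk ratio 0.7 with 250 per arm: 25 against 17.5 events.

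Half-width = 1.96 × √(0.10 × 0.90/250 + 0.07 × 0.93/250) = 1.96 × 0.0249 ≈ 4.9 points, around a difference of 3.0 points. The risk ratio interval is 0.39 to 1.26. At an assumed 20% control risk (50 against 35 events) the difference is 6.0 points, with an interval for the reduction from −0.6 to 12.6 points. Both intervals include no effect, but they show what the trial can and cannot exclude.

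**The case against.** The strongest defence is that description is a deliberate and honest choice. The outcome is not powered, repair decisions are open-label, and there is no multiplicity scheme. A later switch to a model would be a visible departure from the plan, and counts by arm would let any reader compute a crude risk difference. This stands as a reason not to run a confirmatory test. It does not explain why objective (d) and variable 5 are worded as a reduction and a difference, nor does it supply the event comparison that section 10 needs.

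A reader might go further and infer that the expectation of few events is wrong. The documents do not support that:
- The simulation counts diameters, whereas section 8.3 speaks of repairs, ruptures and deaths. The documents do not say what share of crossings leads to repair.
- The results run from few to many, depending on a baseline distribution that is not given.
- Loss may be counted twice. Section 8.4 reads "CT data will likely show 10-15% larger SD, adding a 30% dropout rate over five years", and section 2.1 gives repair as an example of leaving the study, so the 30% may already include repairs.
- Section 1.1 says of patients under surveillance "of whom 70% eventually will require surgical repair", but gives no time frame, so this is not a 60-month rate.

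Nor was the 30% effect derived from repair rates. Section 8.4 takes it from growth data and mentions repair only to explain why the effect matters.

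**Conclusion.** The mismatch between sections 1.2.2 and 8.2.2 on one side and section 8.3 on the other is in the text and does not depend on any event count. The planned method cannot answer objective (d), gives the cost-effectiveness ratio no pre-specified event difference, and leaves the event part of the interim harm rule without a test.

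The expectation of few events is unsupported, not disproved. It is reasonable at 24 months. At 60 months it is uncertain: about 24 to 165 crossings of 500 at the protocol's mean growth over the four assumed baselines, and as few as 6 at an assumed 2 mm/year, with repairs possibly fewer. All of these counts rest on assumed baselines, constant growth, independent 30% loss and 55 mm for everyone. This should be corrected, but it does not affect the primary analysis.

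**What to change.** In section 8.3, for variable 5 only, pre-specify a between-arm risk difference (or ratio) with 95% CI at 60 months, by randomised arm, for one stated event definition. Say which imaging method defines the diameter if diameter is part of the event, and how patients lost without an event are counted. Present the result as an estimate, not a confirmatory test. Adjustment for baseline diameter is optional.

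Reconcile the need-for-surgery definition in section 1.2.2 with the sex-specific thresholds in section 1.1. Use the same event comparison for the harm rule in section 10.

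If the sponsor prefers description only, relabel objective (d) and variable 5 as descriptive; the interim harm rule would still need a named event comparison.

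The cost is a few lines of text and one definition, with no new visits or scans. Section 4.2 asks for completion imaging on early withdrawal only where possible, so some statuses will be missing and the rule for lost patients matters. The downsides are one more secondary comparison without a multiplicity scheme, an event partly driven by open-label repair decisions, and possibly a wide interval, as in the 10% example.
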